## **Confounding variables**

Diabetes mellitus, immunosuppression, comorbidities, surgeon, degree of contamination, elective vs. Emergency surgery, length of surgery, intra-operative blood loss, wound protectors, mesh, 'take-backs / re-operations', antibiotics (other than for prophylaxis).

## **Definition of SSI (as per CDC Criteria) **

An infection is defined by the CDC as being the presence of at least one of the following:

1. Purulent drainage, with or without laboratory confirmation, from within the wound
2. Organisms isolated from an aseptically obtained culture of fluid from the incision
3. At least one of the following signs or symptoms of infection: pain or tenderness, localized swelling, redness and superficial incision deliberately opened by the surgeon, unless incision is culture-negative
4. Diagnosis of superficial incisional SSI by the independent assessor

## **Power and sample size estimation**

SSI is highest in colorectal surgery with a reported cumulative incidence of 9.5% . Over the last decade, there has been emerging evidence in success of wound management devices in reduction of the burden of post-operative wound infections to as low as 0 % . Two recent studies using Prevena™ for incisional negative pressure therapy have reported significant reduction in wound

infection rates from 30% to 6% for groin vascular surgery and from 16% to 4% for sternotomy incisions in cardiac surgery respectively .

Assuming an overall incidence of SSI is about 15% for the range of abdominal surgery, and a rate of 3% for clean cases, we have calculated that we will need 89 patients in each arm of the study group, to provide a significant difference with a power of 80%. We have estimated this to provide a relative risk reduction of about 80% in keeping with existing evidence on Prevena™.

A two group  $\chi^2$  test with a 0.050 two-sided significance level will have 80% power to detect the difference between the control arm, of **0.150** and intervention arm of **0.030** (odds ratio of 0.1752) when the sample size in each group is **89**. (NB: We have obtained expert statistical help from our hospital statistician regarding sample size calculation).

#### Study procedures:

This is an investigator-initiated study and the devices will be funded by Kinetics Concepts Inc, KCI, Australia. Prevena™ is a licensed product entered onto the Australian Register of Therapeutic Goods (TGA ARTG certificate: **2156636**). Patients enrolled into the study will be counselled and a patient information brochure about the research project provided as part of informed consent. Risks associated with use of the device / dressing is expected to be negligible. Any grievances / complaints will be referred to the hospital Patient Representative Department and the study doctor(s) will aim to resolve the same within an acceptable period of time.

#### Expected outcomes:

We anticipate our study will provide high quality evidence regarding usage of topical negative pressure therapy as a primary incisional therapy for abdominal surgery. It could potentially identify specific target groups where benefits will be maximal and cost-effective.

#### Logistics:

Enrolled patients will be assigned unique study number for purpose of data protection and confidentiality. Randomisation will be securely kept in a sealed envelope tagged onto consent form and be made available to surgeon upon completion of wound closure. The same will be made available by the study doctor(s) in the event of accidental loss of the sealed envelope (using the unique number). Patients who satisfy the entry criteria and consent to the study will be randomised in blocks of 8 to either control or intervention arm.

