#### **Inclusion Criteria**

1. Patients (over age of 16 years) undergoing elective and emergency laparotomy
2. Type of wounds - clean contaminated, contaminated and dirty

[Note: Patients who have had previous laparotomy including those who may have mesh implants in the site of proposed surgical incision and those patients with pre-existing stoma will also be considered for our study]

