## **Methodology**

Informed consent will be taken from eligible patients participating in our study. Data will be collected prospectively on a standardised proforma (see *appendix i*) and then entered into a MS Excel database. A computer assisted randomisation will be used to assign patients to either the control (standard dressing) or interventional arm (TNP dressing). This will be made available to the operating surgeon only upon completion of skin closure to avoid performance bias. Wound closure will be by sutures or skin staples as per surgeon's preference. Stoma nurse(s) attached to our department will be independent assessor of the wounds. Wounds will be assessed on post-operative day 5-7 and again in 1 month's time. We propose to use SPSS for statistical analysis. We also aim to perform an intention to treat analysis in event of violation of research protocol.

Type of standard dressing (control arm)                      Standard Hospital Dressings  
(Comfeel / Cutiplast / Post-op Visible)

Type of TNP dressing (interventional arm)                      **Prevena™ Peel & Place™ Therapy,**  
(KCI, Australia)

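### Concealment until skin closure is intended but weakly protected: the envelope stays with the patient's consent form and the study doctors can reach the number-to-arm key

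*Protocol*

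**What the plan says.** The Methodology section specifies a computer-assisted sequence and says that the allocation is "made available to the operating surgeon only upon completion of skin closure to avoid performance bias". The same section leaves the choice between sutures and staples to the surgeon. The Type of study section describes the trial as non-blinded.

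The Logistics section describes how the allocation is kept: "Randomisation will be securely kept in a sealed envelope tagged onto consent form and be made available to surgeon upon completion of wound closure". If the envelope is lost, there is a back-up: "The same will be made available by the study doctor(s) in the event of accidental loss of the sealed envelope (using the unique number"). Under the same heading, those meeting the entry criteria and giving consent are "randomised in blocks of 8 to either control or intervention arm".

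The Inclusion Criteria limit entry by wound class: "Type of wounds - clean contaminated, contaminated and dirty". Elective and emergency laparotomies are both eligible.

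**The concern.** In a non-blinded trial, withholding the arm until the wound is closed is the protocol's main safeguard at the point of treatment. The safeguard is only as strong as the custody of the envelope and of the list behind it.

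Two features weaken that custody. The envelope is attached to a document belonging to one identified patient, and no separate storage is described. The study doctors can also recover an arm from a study number, so a key exists within the study team, and nothing says it is held apart from those who recruit, operate or assess.

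Anyone who learned the arm early could affect the choice of closure or the judgement on wound class. Someone able to consult the key ahead of time could also affect who is enrolled. These are the selection and performance biases that late release is meant to prevent, and analysis cannot reliably repair them afterwards.

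**Working it through.** **1. The two sections side by side**

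| Question | Methodology | Logistics |
|---|---|---|
| How is the sequence made? | Computer assisted | Blocks of 8 |
| When does the surgeon learn the arm? | After skin closure | After wound closure |
| Where is the allocation kept? | Not stated | Sealed envelope on the consent form |
| Who else can reveal it? | Not stated | Study doctor(s), by study number, if the envelope is lost |
| Who independent holds the list? | Not stated | Not stated |

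The sections agree on the aim and the timing of release. The weakness is in the last three rows.

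**2. What follows directly and what is inferred**

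- Follows directly: the study doctors can obtain an arm from a study number. The only stated use is a lost envelope, but the procedure could not work without a key that covers every patient.
- Inferred: the envelope is with the clinical team before or during surgery. This is the natural reading of "Randomisation will be securely kept in a sealed envelope tagged onto consent form", but the time of attachment is not given.
- Not stated either way: whether the study doctors recruit, operate or assess.

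**3. Does the sample size depend on this?**

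Inputs from the Power and sample size estimation section: 15% v 3%, two-sided 0.05, 80% power, uncorrected chi-square. The mean proportion is (0.15 + 0.03)/2 = 0.09.

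n = [1.960 × √(2 × 0.09 × 0.91) + 0.842 × √(0.15 × 0.85 + 0.03 × 0.97)]² / 0.12²
= [1.960 × 0.4047 + 0.842 × 0.3957]² / 0.0144 = 88.1, rounded up to **89 per arm**.

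Power at 89 is 80.4%. The odds ratio is (0.03/0.97)/(0.15/0.85) = 0.1753, against 0.1752 in the protocol. The protocol's figures reproduce, and none changes if custody is improved.

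**4. How few events carry the result**

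Expected infections are 89 × 0.15 = 13.35 and 89 × 0.03 = 2.67, about 13 v 3. Pearson chi-square without correction, 89 per arm:

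| Control v intervention | p |
|---|---|
| 13 v 3 (expected) | 0.009 |
| 13 v 4 | 0.022 |
| 13 v 5 | 0.047 |
| 13 v 6 | 0.089 |
| 12 v 4 (one infected patient changes arm) | 0.036 |
| 11 v 5 (two infected patients change arm) | 0.12 |

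Starting from the expected result, significance is lost with three more intervention-arm infections, or with two infected patients changing arm while the arms stay at 89. The table shows that the result rests on few events. It does not measure bias from weak concealment.

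**5. Block size as an aggravating factor**

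Assume 4:4 allocation within each block of 8, a single list, and full knowledge of earlier arms in the block. Over the 70 possible blocks, an average of 1.6 of 8 assignments (20%) are certain in advance. Best guessing is right for 5.33 of 8 (66.6%, against 50% by chance). With separate lists or incomplete knowledge of earlier arms the figures would differ. The protocol settles neither point.

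**The case against.** The strongest reply is that the protocol does describe concealment: a computer-made sequence, a sealed envelope, and release after closure, stated consistently in two sections. This stands. A reader might infer that allocation is simply not concealed, or that Logistics contradicts Methodology, and the text supports neither reading. Early opening of the envelope would be a breach of the protocol, not its plan.

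A reader might also infer that the people enrolling patients hold the list. The text gives the study doctors access only for a lost envelope and does not say what other roles they have. Some back-up for a lost envelope is needed, and having one is not a defect. What remains is that the back-up is not separated from the study team.

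The selection route needs care. An envelope attached to a consent form belongs to someone who already has a form, so it cannot by itself steer who is approached. That would require consulting the key, or guessing from the block.

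On eligibility, wound class may be settled only at operation, so an allocation tied to the patient earlier could use up a place in the sequence for someone later found ineligible. If the envelope is still sealed at that point, the exclusion is made without knowledge of the arm. It disturbs block balance but does not by itself bias the comparison. Nor does the protocol say that randomisation precedes knowledge of wound class.

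Finally, a reader might take the small event counts to mean that steering one or two patients would decide the trial. From 13 v 3, one infected patient changing arm leaves p = 0.036. Two such changes, or three added intervention-arm infections, are needed to lose significance.

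**Conclusion.** The point holds as a weakness in safeguards that should be fixed. The protocol intends the arm to be unknown until skin closure. It nevertheless keeps the envelope with the patient's own form, lets the study doctors recover the arm from the study number, and names no independent custodian. The non-blinded design, the surgeon's choice of closure and the stated fixed block of 8 make this matter more.

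The conclusion rests on what the protocol states about custody and on the absence of any stated separation of roles. It does not depend on the envelope being attached before surgery or on the study doctors being recruiters, neither of which is stated. The resulting bias cannot be sized from the document. The planned 89 per arm stands.

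**What to change.** Amend the Logistics section as follows:

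- **Custody.** The list, and any replacement for a lost envelope, are held by someone outside recruitment, surgery and wound assessment. The hospital statistician is one option, although the protocol credits that person only with help on the sample size. Sealed duplicate envelopes kept at each site are another.
- **Envelopes.** Use sequentially numbered opaque envelopes, stored apart from the consent forms.
- **Timing.** Take and open the next envelope only after eligibility, including wound class, and skin closure have been recorded with a time. Count the patient as randomised from that moment.
- **Log.** Record each opening and each use of the back-up.

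The cost is a short amendment and some out-of-hours arrangements, since four hospitals and emergency cases are involved. Sealed duplicates at each site would avoid the need for a custodian on call at all hours. The sample size and the comparison are unchanged.

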### Population / setting (anticipated number / ages / where / by whom):

#### **Setting**

Patients admitted to the Department of Surgery in Westmead (Public), Blacktown (Public), Norwest Private and Westmead Private Hospitals. Surgeons from the above hospitals, including those participating in Acute Surgical Roster will be invited to participate in our study.

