**Anticipated number**

**178 patients**

## **Type of study**

Prospective, non-blinded, randomised controlled study (RCT)

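### A single block size of 8, fixed in the protocol of a non-blinded trial, lets a well-placed observer deduce up to a fifth of the allocations

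*Protocol*

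**What the plan says.** The Logistics section of the protocol fixes the allocation scheme: "Patients who satisfy the entry criteria and consent to the study will be randomised in blocks of 8 to either control or intervention arm". It gives one size and does not mention varying it. The Type of study entry describes the trial as "Prospective, non-blinded, randomised controlled study (RCT)".

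Two safeguards are stated. Logistics says "Randomisation will be securely kept in a sealed envelope tagged onto consent form", and Methodology says of the allocation: "This will be made available to the operating surgeon only upon completion of skin closure to avoid performance bias". Logistics adds a second route to the allocation: "The same will be made available by the study doctor(s) in the event of accidental loss of the sealed envelope (using the unique number)".

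The Setting section covers four hospitals: "Westmead (Public), Blacktown (Public), Norwest Private and Westmead Private Hospitals". Neither that section nor Logistics says whether there is one list for all four or a separate list for each.

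**The concern.** Blocking forces the arms to be equal at the end of every block. If the block length is known and constant, the last allocations in a block follow from the earlier ones. In a blinded trial this does little harm, because the earlier allocations are hidden. Here they are not: a negative pressure dressing and a standard dressing can be told apart on the ward.

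Two things are at stake. First, a recruiter who can foresee the next arm can, knowingly or not, choose which patient to approach next. The resulting selection bias cannot be reliably repaired in the analysis. Second, the protocol withholds the allocation until the skin is closed in order to prevent performance bias. That protection works only if the allocation cannot be inferred beforehand. Methodology leaves the choice of sutures or staples to the surgeon, so there is at least one decision before disclosure that a foreseen allocation could affect.

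**Working it through.** **Inputs.** Block size 8 (Logistics); 178 patients, 89 per arm (Anticipated number; Power and sample size estimation). Assumption: each block holds four of each arm. The protocol does not say so, but equal arms of 89 imply 1:1 allocation.

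**The plan's own figure.** With 15% v 3%, two-sided 5% and 80% power, the pooled chi-square formula without continuity correction gives n = [1.96·√(2·0.09·0.91) + 0.8416·√(0.15·0.85 + 0.03·0.97)]² / 0.12² = 88.1, so 89 per arm. The stated sample size reproduces, and nothing below changes it.

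**Certain allocations.** There are C(8,4) = 70 equally likely blocks. The allocation at position k is certain when one arm already has its four patients among the first k − 1, which has probability 2·C(k−1, 4)/70 for k = 5, 6, 7. Position 8 is always certain.

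| Position | Probability that it is certain |
|---|---|
| 1 to 4 | 0 |
| 5 | 2·1/70 = 2.9% |
| 6 | 2·5/70 = 14.3% |
| 7 | 2·15/70 = 42.9% |
| 8 | 100% |

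Sum: 0.029 + 0.143 + 0.429 + 1 = 1.6 of 8, or 20%. Over the trial, 0.20 × 178 = 35.6. Counting only the 22 complete blocks (178 = 22 × 8 + 2) gives 22 × 1.6 = 35.2. Either way it is about 35 to 36 patients.

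**Best guess.** An observer who always names the arm with more places left is right with probability 0.500, 0.571, 0.571, 0.629, 0.629, 0.714, 0.714 and 1.000 at positions 1 to 8. The sum is 5.33 of 8, or 67%. Over positions 5 to 8 it is (0.629 + 0.714 + 0.714 + 1)/4 = 76%.

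**Comparison with other fixed sizes.** The same enumeration gives a certain share of 33% for blocks of 4, 25% for blocks of 6 and 14% for blocks of 12. A longer fixed block lowers the figure but does not remove it.

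**Effect of late disclosure.** Suppose the immediately preceding patient's envelope is still sealed when the next patient is considered. The observer then knows only k − 2 allocations at position k, and each probability in the table moves one position later: 2.9% at position 6, 14.3% at 7 and 42.9% at 8. The sum is 0.6 of 8, or 7.5%. This illustrates that the delay reduces predictability without removing it.

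**The case against.** The strongest reply is that the observer in this calculation may hardly exist. The figures require someone who knows the block boundaries, the order of enrolment and every earlier allocation. A dressing is seen by those who care for that patient, not by everyone who recruits. With four hospitals and many surgeons, including those on the acute roster, one surgeon would rarely see a whole block if blocks run across hospitals. The envelope goes with the consent form and is opened only after closure, so earlier patients in a block may still be undisclosed. Nothing shows that the block size was circulated to recruiters beyond its appearance in the protocol. Eight is also already a fairly long block.

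All of this stands as a limit on size, and it makes 20% and 67% a ceiling. It does not dispose of the point. Study staff who follow all enrolments could hold the information. So could recruiters at one hospital if each hospital has its own blocks, which the protocol leaves open.

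A reader might also infer more than the documents support:

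- **That the lack of stratification is an error.** The Confounding variables section does list "degree of contamination, elective vs. Emergency surgery", and neither enters the randomisation. But it lists about a dozen factors without ranking them, so they cannot be called the strongest known ones. Leaving them to chance in 178 patients is a trade-off. It costs precision and does not bias the comparison.
- **That chance imbalance could make or hide the result.** Under an exact hypergeometric calculation with 89 per arm, the chance that the arms differ by at least 10 percentage points on an unstratified factor is 9%, 19%, 22% or 23% for an assumed prevalence of 20%, 30%, 40% or 50%. If the factor carries an assumed infection risk gap of 10 to 20 points, a 10-point imbalance shifts the difference between arms by 0.10 × 0.10 = 1 point to 0.10 × 0.20 = 2 points, against the planned 15 − 3 = 12.
- **That the final analysis is an unadjusted chi-square.** That test appears in the sample size calculation. The protocol does not name it as the final analysis, and an analysis plan that is not shown may adjust for covariates.

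**Conclusion.** The point holds for the block size alone. A single fixed size is written into the protocol of a non-blinded trial, and concealment until closure does not stop deduction from allocations already revealed. At most, 20% of allocations (1.6 of 8, about 36 of 178) would be certain and 67% of guesses correct. This upper bound assumes 4:4 blocks and an observer with complete knowledge of boundaries and earlier allocations. How close anyone could come to it depends on whether blocks run by hospital, which the protocol does not state. The documents do not show that any allocation was in fact foreseen. The sample size stands, and the documents do not support extending the criticism to stratification or to the form of the analysis.

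**What to change.** In Logistics, replace the reference to blocks of 8 with wording such as: *Patients will be allocated 1:1 from a computer-generated list in permuted blocks of randomly varying size. The sizes are known only to the person who generates the list and do not appear in documents available to investigators.* Add one sentence saying whether the list runs separately in each hospital or across all four. Make sure that the lost-envelope route discloses only the one patient's allocation, so that it does not reveal the block structure.

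The cost is one regenerated list before the first patient and slightly more complex list handling. Varying the sizes does not make guessing impossible, but an observer can no longer count to the end of a block of known length. Stratifying by one or two of the listed factors, with a matching analysis, remains open to the investigators as a design choice and is not needed to correct this point.

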#### Anticipated start / finish dates:

**Anticipated start date** December 2014

**Anticipated finish date** April 2016

### Monitoring / reporting:

A data monitoring steering committee led by is being set up to review progress every 3 months, and updates will be discussed in our 'Westmead Colorectal Research Forum'. We proposed to register the project upon ethics approval for a post-graduate research degree (MS) with University of Sydney Medical School. We aim to disseminate the results as peer reviewed publication(s) in scientific journals and also present in Royal Australasian College of Surgeons (RACS) annual scientific meeting.

### Statement of ethical issues:

We aim to commence recruitment for the research project upon Westmead HREC ethics approval. Suitable measures will be taken for providing adequate interpreters for non-English speaking participants for informed consent. Conduct of research will be according to strict hospital and NSW health regulations.

